7.2. Statistical analysis

Distributions of baseline characteristics for locations and patients will be compared between the intervention or control periods to assess effectiveness of the randomization, and statistical or clinical differences will be adjusted in sensitivity analyses. All analyses for treatment and control periods comparisons will use an intention-to-treat approach and results will be reported used the CONSORT extension to cluster randomized trials.

The primary outcome for this study is 30-day all cause non-elective acute care utilization. Characteristics of the locations and individuals will be summarized by levels of randomization steps, locations, and individuals. The count, rates and 95% confidence intervals of 30-day non-elective acute

care utilization in the control period will be presented and compared with that in the treatment period. The primary analysis will be conducted using generalized linear mixed models with fixed effects for intervention, and intervention multiply by the time, accounting for the cluster randomized trial design with a random cluster (hospitals) or time (steps) effect. We will estimate and report the intra class correlation coefficients for all outcome measures to assess assumptions for sample size analyses and for future investigations using similar designs and outcomes. The primary analyses will follow the intention to treat principle with an additional per protocol analysis including those who actually used VPTC. The secondary analyses will include within cluster comparisons of intervention and control periods (not adjusting for any confounding effect of time), as well as comparisons of a series of (unbalanced) quasi-parallel cluster trials between those enrolled and unenrolled clusters at each intervention enrollment period. The same analyses plan will also be applied to secondary outcomes.

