5.1.2. Secondary Outcome Variables

- a. Demographic characteristics (age, race, gender, insurance plan)
- b. Charlson comorbidity index score
- c. 60-day all cause non-elective acute care utilization (ED visits, observation, and inpatient encounters).
- d. 30-day behavioral health acute care utilization (ED visits, observation, and inpatient encounters).
- e. A behavioral health office visit within 7 days of discharge
- f. An avoidable ED visit within 30 days of discharge

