5.2. Trial Design

5.2.1. Justification for stepped wedge cluster randomized control trial

The primary aim is to assess the effectiveness of a structured multidisciplinary care plan (intervention), compared with usual care (control) on 30-day all cause non-elective acute care utilization (ED visits, observation, and inpatient encounters). The VPTC program will be delivered at the level of location or cluster, thus minimizing contamination and the risk of selection bias, if subjects were randomized at the individual level. Therefore, the unit of randomization and analysis for this study will be the cluster. Considering logistical constraints and design rigor, the intervention will be rolled out sequentially instead of at the same time. Moreover, substantial and differential cluster-effects may exist because of distinct volume and characteristics of patients in each hospital. Thus, the stepped wedge design is advantageous compared with other alternative designs.

The stepped wedge design implies a baseline period, in which no clusters are exposed to the intervention. Then, at the chosen time interval of three months, one location will be randomized to cross from the control to intervention (Figure 1). This process continues until all seven locations have crossed over to the intervention. The order of this cross over process will be randomized. We will use randomization to assign location order so that if a high or low volume location is assigned cluster 1, a high or low volume location is assigned cluster 7. The single ED location will be assigned to cluster 4. SAS Enterprise Guide version 8.2 will be used for the randomization. Allocation will be communicated only to the behavioral health team initially to prevent contamination. Locations will learn of allocation in the month preceding roll-out. Patients in included locations will be blinded to the intervention or control period.

An example of the roll out schedule

Location	August 2021	November 2021	February 2022	May 2022	August 2022	November 2022	February 2023	May 2023
Location 1	0	1	1	1	1	1	1	1
Location 2	0	0	1	1	1	1	1	1
Location 3	0	0	0	1	1	1	1	1
Location 4	0	0	0	0	1	1	1	1
Location 5	0	0	0	0	0	1	1	1
Location 6	0	0	0	0	0	0	1	1
Location 7	0	0	0	0	0	0	0	1

1=Virtual Psychiatric Transition of Care Program; 0=Usual Care

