7. DATA COLLECTION AND REPORTING

Patient demographics, Charlson comorbidity score, and utilization will be obtained from the electronic medical record and billing systems. Data from the initial assessment and follow-up contacts will be stored in HealtheCare, a care management platform in Cerner. Data will be retrieved by an application specialist on the research team. Data may be retrieved retrospective to a patient’s completion of the intervention or

usual care arm of the study. A participation rate can be generated from the count of patients enrolled in the VBHI program over the count of patients meeting the inclusion criteria.

A bi-monthly report will be produced for the intervention arm. The report will be by primary care practice and overall showing the prior 2 weeks of activity.

- Count of patients meeting the inclusion criteria
- Count of patients with a HealtheCare account
- Count of patients enrolled in the VBHI program
- Patient list with their enrollment status in HealtheCare

A monthly report will be produced for the intervention arm. The report will be by primary care practice and overall. Report to be generated 2 weeks after the end of the month showing the prior month of activity.

- Count of patients meeting the inclusion criteria
- Count of patients with a HealtheCare account
- Count of patients enrolled in the VBHI program
- Patient list with their enrollment status in HealtheCare

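### Pre-specify the covariates already being obtained in the primary model, instead of choosing them for a sensitivity analysis from observed differences (minor)

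*Combined protocol and SAP*

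**What the plan says.** Section 7.2 describes the primary analysis as "generalized linear mixed models with fixed effects for intervention, and intervention multiply by the time", "with a random cluster (hospitals) or time (steps) effect". No patient or site covariate is listed.

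Covariates appear elsewhere in the same section. Baseline distributions are to be "compared between the intervention or control periods to assess effectiveness of the randomization", and "statistical or clinical differences will be adjusted in sensitivity analyses". The plan gives no list of covariates and does not say how large a difference counts.

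The data will be to hand. Section 7 states: "Patient demographics, Charlson comorbidity score, and utilization will be obtained from the electronic medical record and billing systems". Section 5.1.2 names age, race, gender and insurance plan, and separately the Charlson index, though it files them under secondary outcomes. Section 7.3 expects some covariate values to be missing.

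Section 5.2.1 expects sites to differ: "substantial and differential cluster-effects may exist because of distinct volume and characteristics of patients in each hospital". It restricts the randomised order by volume at the two ends and fixes the single ED location in fourth place. It does not restrict the order by case mix.

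**The concern.** Two features of this rule are weak.

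First, the trigger does not do what the plan says it does. Sites are randomised, not patients. In the example schedule the first site contributes seven of its eight periods to the intervention and the last site one of eight. A pooled comparison of intervention with control periods is therefore largely a comparison of early-crossing with late-crossing sites. Ordinary differences between hospitals will show up as baseline differences even when randomisation was carried out perfectly, and the adjustment set then comes from the data.

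Second, variables likely to predict acute care use are left out of the primary model although they cost nothing extra to obtain. At stake are some precision and some protection against measured case mix that changes within sites over the eight three-month periods.

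**Working it through.** **Inputs from the documents.** Seven sites, eight periods, one site crossing per step (section 5.2.1). 81 patients per site-period, 20% versus 14%, ICC 0.20, two-sided alpha 0.05, power 0.89 (section 7.1). Diluted intention-to-treat difference 2.4 points; average enrolled cluster 96 at 40% enrolment, so 96/0.40 = 240 eligible per site-period (section 7.1).

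**Assumptions, because the documents give no figure.** Covariate R² of 0.02, 0.05 and 0.10; a covariate with 30% prevalence and site-level ICC of 0.005 to 0.05; 240 patients in every cell.

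**1. The plan's own power.** For a stepped wedge with a random site intercept and fixed period effects,

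Var = I·s²(s² + T·τ²) / [(I·U − W)s² + (U² + I·T·U − T·W − I·V)τ²],

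with I = 7, T = 8, U = 28, W = 140, V = 140. Total variance is 0.20 × 0.80 = 0.16, so τ² = 0.20 × 0.16 = 0.032 and s² = 0.80 × 0.16/81 = 0.00158. The denominator is 56 × 0.00158 + 252 × 0.032 = 8.152, and the numerator is 7 × 0.00158 × 0.2576 = 0.002849. The SE is √(0.002849/8.152) = 0.01869. Power for 0.06 is Φ(3.209 − 1.960) = 0.894, which reproduces the stated 0.89.

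**2. Precision gained by adjustment.** Multiply s² by (1 − R²).

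| R² | SE, 81 per cell (points) | Power, 6 points | SE, 240 per cell (points) | Power, 2.4 points | Interval narrower by |
|---|---|---|---|---|---|
| 0 | 1.869 | 0.894 | 1.088 | 0.597 | – |
| 0.02 | 1.851 | 0.900 | 1.077 | 0.606 | 1.0% |
| 0.05 | 1.822 | 0.909 | 1.060 | 0.619 | 2.5% |
| 0.10 | 1.774 | 0.923 | 1.032 | 0.643 | 5.1% |

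These are risk-difference approximations. In a logistic mixed model, adjustment also changes what the odds ratio is conditional on.

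**3. How often the baseline comparison fires when nothing is wrong.** With k = 7, 6, …, 1 intervention periods per site, site i enters the pooled difference with weight (2k − 8)/28. The squared weights sum to 112/784 = 1/7. Each condition has 28 × 240 = 6,720 patients. Relative to the variance that a test ignoring clustering assumes, the true variance is (1 − ρ) + (ρ/7)/(2/6,720) = 1 + 479ρ, where ρ is the site-level covariate ICC. The chance of p<0.05 is 2Φ(−1.96/√(1 + 479ρ)).

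| ρ | 1 + 479ρ | Formula | Simulation |
|---|---|---|---|
| 0.005 | 3.395 | 29% | 28–29% |
| 0.01 | 5.79 | 42% | 42% |
| 0.02 | 10.58 | 55% | 54–56% |
| 0.05 | 24.95 | 69% | 69% |

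The simulations used 3,000 and 20,000 trials with beta-distributed site prevalences, correct randomisation and no drift.

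**4. Whether that reaches the primary estimate.** The weights that the mixed model gives each cell can be applied to assumed case-mix shifts.

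- Stable site differences, random cluster effect: an error of 0.003 to 0.007 points in the effect per 1-point SD of site risk. They almost cancel.
- Site-specific quarter-to-quarter shifts with SD of 1 to 2 points of risk (assumed): an error SD of 0.47 to 0.94 points with period effects, or 0.31 to 0.62 without, against an expected effect of 2.4 points. Covariates can remove only the share that they explain.

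**The case against.** A reader might infer that the headline odds ratio is unprotected against case-mix imbalance, and might take the 28–69% as the risk to it. The documents do not support that. The rate says how often a baseline comparison fires, and it affects only which covariates enter a sensitivity analysis. A null simulation of the same setting assumed a covariate odds ratio of 2 on a 20% outcome and used site effects in place of the random cluster effect. The estimate without the covariate had a mean error of at most 0.03 points and a false-positive rate of 4.7% to 5.8%, about the same whether or not the comparison had fired. Stable differences matter only if the random effect is placed on time instead of site, when the error is about 0.66 points per 1-point SD of site risk. That belongs to the unsettled model specification.

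A reader might also infer that the plan has no answer if adjusted and unadjusted results disagree. It has one: section 7.2 ranks the mixed model without covariates as primary and the adjusted analysis as sensitivity.

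Other points also stand. The gain in precision is small and rests on an R² that the documents do not give. Section 7.2 does not define a statistical difference, so p<0.05 ignoring clustering is an assumption, although the synopsis's mention of univariate comparisons makes it plausible. Section 7.2 already plans summaries by step and location. The fixed fourth place gives the ED location four periods in each condition, so in equal cells it has zero weight in the pooled comparison.

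The objection does not rescue the use of the comparison as a check on randomisation or as a way of choosing covariates. Nor does it give a reason to leave available predictors out of the primary model.

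**Conclusion.** The point holds as a minor, cheap improvement. The primary analysis without covariates is not invalid by design, and the stated power of 0.89 does not depend on adjustment.

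Two costs remain: no adjustment for measured case mix that shifts within sites over the two years, and a confidence interval about 1% to 5% wider than it need be for R² of 0.02 to 0.10. The drift exposure depends on an assumed size of shift and on how much of it these five variables explain; the documents settle neither. Adjustment does not bring power for the 2.4-point difference to 0.80: it reaches 0.64 at most in this range with 240 per cell.

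The absence of a main period effect and the choice left open between a cluster and a time random effect are separate, numerically larger issues, and covariate adjustment does not solve them.

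**What to change.** In section 7.2:

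- Name age, gender, race, insurance plan and Charlson score as fixed covariates in the primary mixed model, for the primary and secondary outcomes.
- Define each as its value at the index discharge. This matters most for insurance: section 7 allows retrospective retrieval and the programme includes help with financial assistance, so a later value could be affected by the intervention.
- State one rule for missing covariate values in the primary analysis, for example a missing category, with the multiple imputation of section 7.3 as sensitivity.
- Report the model without covariates as the sensitivity analysis.
- Show baseline characteristics by site and period as description only, and remove the rule that selects covariates from observed differences.

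The cost is wording, since these variables are to be obtained in any case. The downsides are that the odds ratio becomes conditional on the covariates, and that missing values, whose extent the plan does not give, must be handled in the primary analysis.

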	
• Navigation to additional psychiatric or substance use services, if needed• Motivational interviewing and brief therapeutic recommendations, if needed
Statistical Analysis	Analyses will include all patients identified as having been discharged and meeting the inclusion criteria. Baseline comparisons of the intervention and usual care groups will be made using univariate analyses. The primary analysis will be conducted using generalized linear mixed models with fixed effects for intervention, and intervention multiply by the time, accounting for the cluster randomized trial design with a random cluster (hospitals) or time (steps) effect. Results will be presented with odds ratios and 95% confidence intervals.

LIST OF ABBREVIATIONS

BHI	Behavioral Health Integration
CORE	Center for Outcomes Research and Evaluation
C-SSRS	Columbia – Suicide Severity Rating Scale
EDW	Enterprise Data Warehouse
VPTC	Virtual Psychiatric Transition of Care
NC	North Carolina
PHI	Private Health Information
PHQ-2	Patient Health Questionnaire - Screener for Depressive Disorders
PHQ-9	Patient Health Questionnaire – Screener for Severity of Depression
SOP	Standard Operating Procedures

TABLE OF CONTENTS

1.1.	Hypothesis.....	8
1.2.	Primary Objective	8
1.3.	Secondary Objectives	8
1.4.	Exploratory Analyses	8
2.	BACKGROUND	9
3.	RATIONALE	9
4.	SUBJECT AND SITE SELECTION	10
4.1.	Accrual.....	10
4.2.	Accrual – Subjects	10
4.3.	Participating sites	10
4.4.	Inclusion\Exclusion Criteria	11
4.4.1.	Inclusion Criteria	11
4.4.2.	Exclusion Criteria	11
4.5.	Evaluable Population	11
5.	OVERALL DESIGN.....	11
5.1.	Variables	11
5.1.1.	Primary Outcome Variable.....	11
5.1.2.	Secondary Outcome Variables	11
5.1.3.	Exploratory Variables	12
5.2.	Trial Design	12
5.2.1.	Justification for stepped wedge cluster randomized control trial	12
5.2.2.	Virtual Psychiatric Transition of Care Program	13
5.2.2.1.	Zero Suicide Pathway	13
5.2.2.2.	VPTC Pathway	13
5.3.	Patient Graduation from the VPTC Program	14
5.4.	Continuation of the Intervention	14
6.	QUALITATIVE REVIEW	14
7.	DATA COLLECTION AND REPORTING.....	15
7.1.	Sample Size Analysis	16
7.2.	Statistical analysis	16
7.3.	Missing Data	17
7.4.	Training	17
7.5.	Data Collection Dates.....	17

8. INTERVENTION PLAN.....	18
8.1. Behavioral Health Professional Assessments.....	18
8.2. Follow-up Assessments.....	18
8.3. Psychiatric Virtual Appointments.....	18
9. STUDY GOVERNANCE	19
10. SAFETY RISKS AND REPORTING.....	19

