7.1. Sample Size Analysis

Calculations of sample size were based on primary analysis of 30-day non-elective acute care utilization on a binary group. Our preliminary data shows that average unique patients in each hospital (cluster size) per three months ranged from 159 to 300, we expected an enrollment rate of 40%. Thus, the average effective cluster size is 96 with a standard deviation of 15. Conservatively, we would at least expect an average cluster size of 81. With the assumption of detecting a change from 20% in the control period to 14% in the intervention period for 30-day non-elective acute care utilization, a mean cluster size of 81 with seven clusters and seven steps (8 time periods inclusive of a control period) would achieve a power of 0.89 if intra-class correlation coefficients (ICC)=0.20 and two-side $\alpha=0.05$. Holding other parameters constant, the larger ICC is, the higher the power we will obtain. The coefficient of variation (CV) of sample size is approximately 0.15. To account for this varying cluster size, we inflated the number of patients by 10% resulting in an average cluster size of 89 patients per three months, resulting in a sample size of 2,495 patients among the intervention group and 4,990 patients overall inclusive of our control population. In this pragmatic trial, those assigned to the intervention but did not enroll in VPTC during the intervention period (around 60%) would also be counted in the intervention arm. It is within our expectation that intervention arm eventually has smaller reduction in 30-day non-elective acute care utilization (i.e. $0.4*0.14 + 0.6*0.20 = 17.6\%$, difference=2.4%). However, we still ensure a power above 0.80 as long as over 2,495 patients actually received VPTC. The power was calculated by using the PASS 15.

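### Section 7.2 compares control-period with treatment-period rates without saying that location or calendar period is allowed for, although the roll-out gives the two groups very different hospital mixes

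*Combined protocol and SAP*

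**What the plan says.** Section 7.2 (Statistical analysis) plans a control-versus-treatment summary of the primary outcome, made up of event counts, rates and their 95% CIs. It states that "care utilization in the control period will be presented and compared with that in the treatment period". No CI method is given, and nothing is said about location or calendar period for these figures.

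The sentence that follows introduces the generalized linear mixed model as the primary analysis. Allowance for the cluster design is attached to that model, through a random effect for hospital or for step. Within-location comparisons and step-by-step comparisons between crossed and uncrossed locations come later, as separate secondary analyses. The same plan is extended to the secondary outcomes.

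On reporting, the Statistical Analysis row of the synopsis states: "Results will be presented with odds ratios and 95% confidence intervals". Section 7.1 sizes the trial on "detecting a change from 20% in the control period to 14% in the intervention period", with power stated "if intra-class correlation coefficients (ICC)=0.20". It then expects 17.6% in the intervention arm under intention to treat, a difference of 2.4 pp, because about 60% of patients there will not enrol.

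**The concern.** In a stepped wedge, condition is tied to both location and time. In the example schedule of Section 5.2.1, Location 1 has one control quarter and seven intervention quarters, and Location 7 the opposite. A rate pooled over all treatment quarters is therefore dominated by early-crossing hospitals, and a rate pooled over all control quarters by late-crossing ones. If hospitals differ in baseline utilization, the two rates differ even when the program does nothing. Section 5.2.1 itself expects substantial differences between clusters.

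The rate comparison would stand beside the mixed-model odds ratio. It could show an apparent benefit or harm that only reflects which hospitals crossed early, and so contradict the model. The plan does not say which result governs the description of the effect in absolute terms.

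**Working it through.** **Inputs from the plan.** 7 locations and 8 quarters, one crossing per quarter (Section 5.2.1). From Section 7.1: 20% control rate, ICC 0.20, 81 patients per location-quarter for power, inflated by 10%; 2,495 patients per condition; average enrolled cluster size 96 at 40% enrolment.

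**Assumptions added.** Equal volumes, no program effect, no calendar trend, and ICC on the proportion scale with total variance 0.20 × 0.80 = 0.16.

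**1. Reproduce the plan's power.** Section 7.1 states that the design "would achieve a power of 0.89 if intra-class correlation coefficients (ICC)=0.20". The Hussey-Hughes variance is

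I·s²(s² + T·t²) / [(I·U − W)s² + (U² + I·T·U − T·W − I·V)t²],

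with I = 7, T = 8, U = 28, W = V = 140, t² = 0.20 × 0.16 = 0.032 and s² = 0.80 × 0.16/81 = 0.00158.

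- Numerator: 7 × 0.00158 × (0.00158 + 0.256) = 0.00285.
- Denominator: 56 × 0.00158 + 252 × 0.032 = 8.152.
- SE = 0.0187; power = Φ(0.06/0.0187 − 1.96) = 0.894, against 0.89 stated.

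The sample size also reproduces: 81 × 1.1 = 89.1; × 28 = 2,495; × 56 = 4,990. The ICC and variance used below are therefore consistent with the plan's own calculation.

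**2. Location weights in the pooled difference.** Each condition has 28 location-quarters. The location crossing at step k has 8 − k treatment and k control quarters, so its weight in (pooled treatment − pooled control) is (8 − 2k)/28, that is (6, 4, 2, 0, −2, −4, −6)/28. The sum of squares is 112/784 = 0.1429.

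**3. Variation from location mix alone.** SD = √(0.1429 × 0.20 × 0.16) = 0.0676, or 6.8 pp. The chance that this alone exceeds 2.4 pp in either direction is 2[1 − Φ(0.024/0.0676)] = 0.72. This step needs no assumption about the CI method.

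**4. Effect on ordinary binomial CIs.** With n per condition:

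- binomial SE of the difference = √(2 × 0.16/n);
- true SD = √(0.1429 × ICC × 0.16 + (1 − ICC) × 0.16 × 2/n);
- chance that a CI for the difference excludes zero = 2[1 − Φ(1.96 × binomial SE/true SD)];
- chance that the two separate CIs do not overlap: the same, with 2 × 1.96 × √(0.16/n) over the true SD.

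Two sizes are used: n = 2,495 (the plan's figure), and n = 6,720 for all eligible discharges (96/0.40 = 240 per location-quarter, × 28). The binomial half-widths for the difference are 2.2 pp and 1.35 pp.

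| ICC | SD from location mix | CI for difference excludes zero (2,495 / 6,720) | Separate CIs do not overlap (2,495 / 6,720) |
|---|---|---|---|
| 0.20 | 6.8 pp | 75% / 84% | 65% / 78% |
| 0.05 | 3.4 pp | 53% / 69% | 38% / 58% |
| 0.02 | 2.1 pp | 36% / 55% | 19% / 39% |
| 0.01 | 1.5 pp | 24% / 42% | 10% / 25% |
| 0 | 0 | 5% / 5% | 0.6% / 0.6% |

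Beta-binomial simulation (40,000 trials per setting) at ICC 0.20, with equal and with unequal location volumes, gave 74.5–75.0% at 89 per location-quarter and 83.7–83.9% at 223–230.

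**5. After adjustment.** In the same simulations at ICC 0.20, a location-stratified difference rejected in 4.8–5.2% of null trials with no trend. A location-plus-period adjusted difference rejected in 5.0% (89 per location-quarter) and 5.3% (223).

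**6. Calendar time.** Averaged over the schedule, treatment location-quarters fall in quarter 6.0 of 8 and control ones in quarter 3.0. Any trend would add a bias that is not in the figures above.

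**The case against.** The plan never says that clustering is ignored. Section 5.2.1 names the cluster as the unit of analysis, and Section 7.2 promises reporting under the CONSORT extension for cluster trials. Both are general statements, though, and neither says how these particular rates or intervals treat location or period. So the binomial percentages must stay conditional. A reader might infer that the plan commits to naive intervals; the documents are silent.

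Section 7.2 also describes a CI for each rate, not a CI or test for their difference. That is right, and it is why the non-overlap figures are given.

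The comparison is not the primary analysis and no decision rule rests on it. A reader might take 75–84% as the trial's false-positive rate; it is not, because the mixed model is named as primary.

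A reader might also conclude that the pooled rates are the only absolute figures and the odds ratio the only adjusted result. The documents do not establish this: the planned within-location comparisons remove location mix (though expressly not time), and neither their scale nor that of the step-by-step comparisons is stated. Nor was the trial sized on 20% versus 17.6%; it was sized on 20% versus 14%, and 17.6% is the dilution expected under intention to treat.

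Finally, the randomization is constrained. Section 5.2.1 links the volume class of the first and last locations, which carry 72/112 = 64% of the squared weight, and puts the ED location at step 4, where its weight is zero. If linked locations had correlated outcomes (r = 0.5 assumed), the 75–84% would become about 70–81%. Volume matching does not in itself balance baseline event rates.

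**Conclusion.** The concern holds as a gap in specification with a misleading default. Taken as written, the comparison pools different hospital mixes and different calendar periods. The main result is the 6.8 pp SD at ICC 0.20: location mix alone would exceed the expected 2.4 pp difference in about 72% of null trials, and a better interval around each pooled rate would not remove that.

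The 75–84% is conditional on ordinary binomial CIs and on an interval for the pooled difference, neither of which the plan states. All these figures rest on equal volumes, no effect and no trend. They depend strongly on the ICC, for which 0.20 is the plan's own value. The primary mixed-model analysis is not called into question by this point; what is at risk is a rate comparison printed beside it that can disagree with it.

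**What to change.** Replace the sentence in Section 7.2 as follows.

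- Present raw counts and rates by location and quarter, labelled descriptive, with no pooled control-versus-treatment comparison.
- For that comparison, report the standardised 30-day rate under each condition, both averaged over the same set of locations and quarters, and their risk difference with 95% CI, from the primary mixed model and beside the odds ratio.
- State that this model contains both location and calendar period. The present wording offers a random effect for hospital or for step, which does not guarantee both.
- Do the same for the binary secondary outcomes, and carry the change into the synopsis.

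The cost is SAP wording and a little post-estimation code; no new data are needed. The intervals will be wider and look less favourable than ordinary binomial ones.

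### The primary stepped-wedge model lists no main effect of time and leaves the random effect, time coding and reported contrast open, so it allows both drift-confounded and drift-adjusted odds ratios.

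*Combined protocol and SAP*

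**What the plan says.** Section 7.2 of the combined protocol and SAP specifies "generalized linear mixed models with fixed effects for intervention, and intervention multiply by the time", and the synopsis repeats "fixed effects for intervention, and intervention multiply by the time". The random part is given as "with a random cluster (hospitals) or time (steps) effect". No section adds a main effect of time. None says whether time is linear or categorical, whether it is calendar quarter or time since go-live, or where its zero lies. The synopsis states "Results will be presented with odds ratios and 95% confidence intervals" but does not name the coefficient or combination of coefficients that is the primary odds ratio.

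Four other statements bear on intent:

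- Section 7.2 describes a secondary within-site comparison as "not adjusting for any confounding effect of time".
- The same section adds "comparisons of a series of (unbalanced) quasi-parallel cluster trials", which compare sites within the same period.
- It also says "We will estimate and report the intra class correlation coefficients for all outcome measures".
- Section 5.2.1 warns that "substantial and differential cluster-effects may exist because of distinct volume and characteristics of patients in each hospital".

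**The concern.** In the roll-out schedule of section 5.2.1 every site moves from usual care to the program and none moves back. Exposure is therefore tied to calendar time, and separating the two is the main task of a stepped-wedge analysis. A direct reading of the listed terms, with intervention as a 0/1 indicator, forces a flat usual-care rate over the eight quarters. Any change in acute care use for other reasons between August 2021 and July 2023 then has to be absorbed by the intervention terms.

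The size and sign of the error depend on choices the plan does not make. Section 7.1 expects an effect of only 2.4 points once non-enrolment is counted, so a modest drift could imitate or hide it.

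**Working it through.** **Inputs.** From section 7.1: 7 sites, 8 periods, 81 patients per site-period, 20% versus 14%, ICC 0.20, two-sided alpha 0.05, stated power 0.89, 10% inflation, 40% enrolment, diluted difference 2.4 points. From section 5.2.1: the 7 x 8 roll-out table. Eligible patients per site-quarter: 81 x 1.1 / 0.40 = 222.75, about 223. Assumed because the documents do not give it: the secular drift. ICC is varied over 0.01-0.20. Results use generalized least squares (GLS) on the risk scale with normal approximations and no site-by-quarter variation.

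**1. The plan's 0.89.** Take a random site effect, fixed periods and one intervention indicator. The design totals are U = 28, W = 140, V = 140, and the variance of the effect is

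I s2 (s2 + T t2) / [(IU - W) s2 + (U^2 + ITU - TW - IV) t2]

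with s2 = 0.16 x 0.80 / 81 = 0.00158 and t2 = 0.16 x 0.20 = 0.032. The brackets are 196 - 140 = 56 and 784 + 1568 - 1120 - 980 = 252. The SE is 0.0187, 0.06 / 0.0187 = 3.21, and power is 0.894. Six variance conventions give 0.82-0.96. Ignoring time gives 0.99 or more. The listed terms with 0/1 coding give 0.46-0.67 for the intervention coefficient with time 0 to 7, and 0.99 or more for the averaged contrast.

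**2. Timing.** There are 28 treated cells (mean step 5.0, counting from 0) and 28 untreated cells (mean step 2.0). Within each site the gap is exactly 4.0 quarters.

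**3. Bias with a 0/1 indicator.** Fit [1, x, x*t] with a random site effect to data with no program effect and a drift of 1 unit per quarter, with 222.75 patients per cell:

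| Reported quantity | Bias / drift per quarter, ICC 0.01 to 0.20 |
|---|---|
| Average over treated quarters | 3.51 to 3.55 |
| Intervention coefficient, time 0-7 | -0.98 to -0.89 |
| Intervention coefficient, time 1-8 | -1.88 to -1.78 |
| Intervention coefficient, time centred | 2.17 to 2.22 |
| Intervention coefficient, time since go-live | 2.61 to 2.66 |
| Fixed quarters, one indicator | 0.00 |

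The 0-7 coefficient refers to the baseline quarter, when no site is treated.

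**4. False positives under assumed drifts.** For a fall from 20% to 18%, drift is 2 / 7 = 0.286 points per quarter. At ICC 0.02 the bias is 3.53 x 0.286 = 1.01 points. The GLS standard error is 0.83 points, so z = 1.22 and the rejection rate is Phi(1.22 - 1.96) + Phi(-1.22 - 1.96) = 0.23. Varying the final rate:

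| Assumed fall from 20% to | ICC 0.02 | ICC 0.20 |
|---|---|---|
| 19% | 9% | 9-11% |
| 18% | 23-24% | 23-28% |
| 17% | 44-47% | 44-55% |
| 15.8% | 72-76% | 72-84% |

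The ranges reflect how the ICC and the event rate are turned into variances. Over 159-300 patients per cell, the 18% row runs from 18% to 36%.

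**5. Intervention as a two-level factor.** The same two listed terms now give an intercept and a time slope in each arm. Those columns span the same space as 1, x, t and x*t. The linear-drift bias is 0.00 for the averaged contrast and for the 0-7 coefficient. If time is linear, non-linear drift can still leak through.

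**6. Estimability.** With fixed quarters, site effects and a categorical intervention-by-time term, the design has 21 columns and rank 20, because all seven sites are treated in quarter 8.

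**7. Power after adjustment for 2.4 points.** Put s2 = 0.16 x 0.98 / 222.75 and t2 = 0.0032 (ICC 0.02) into the formula of step 1. The SE is 1.24 points, 2.4 / 1.24 = 1.94, and power is 0.49. Across ICCs and conventions it is 0.48-0.61 (0.36-0.47 at 159 per cell, 0.60-0.74 at 300). Keeping a linear interaction and reporting the average over treated quarters gives 0.31-0.41.

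**The case against.** The strongest reply is that the plan meant to adjust for time and worded it loosely. Singling out one secondary analysis as unadjusted for time implies that the primary one adjusts. The quasi-parallel comparisons control time by design. The 0.89 is compatible with fixed periods. This stands as evidence of intent, but 0.894 is the result of one variance convention out of six, so it supports the reading without proving it. Nor do protected secondary analyses repair the primary one.

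A second reply is that the listed terms need not be confounded at all, because factor coding removes linear drift. That is correct. A reader might infer that the primary odds ratio is confounded however time is coded, or that the sponsor chose not to adjust. The documents support neither. What remains is that the result depends on a coding convention the plan does not state: section 5.2.1 names software for the randomization only.

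A third reply is that the drift is hypothetical. It is, so the false-positive rates in step 4 illustrate one reading and do not measure an error in the plan. The documents also give no reason to assume a constant rate over two years.

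Finally, a random time effect alone is permitted by the wording but unlikely to be meant, since ICCs are to be reported for every outcome and large site effects are expected.

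**Conclusion.** The concern holds as an under-specified primary model that must be fixed before analysis. As written, one sentence allows primary results that differ in size and sign:

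- With a 0/1 indicator and a random site effect, about 3.5 times the drift per quarter enters the averaged contrast, and -0.9 to -1.0 times enters the 0-7 coefficient.
- With a two-level factor, linear drift is removed.
- With random time alone, the site clustering that section 5.2.1 expects is dropped.

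The bias multiples follow from the roll-out table, the cell size derived from section 7.1 and ICCs of 0.01-0.20. The 23-28% false-positive figure also rests on an assumed fall of 2 points. With no drift, this bias is absent. Time adjustment was probably intended, but it is not written into the primary model.

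**What to change.** Amend section 7.2 and the synopsis together:

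- (a) Add categorical fixed effects for the eight quarters.
- (b) Always include a random site effect. A random time or site-by-quarter term may be added to it, not substituted for it.
- (c) Name the one contrast reported as the primary odds ratio. The simplest choice is a single intervention indicator, with the intervention-by-time term as a secondary analysis.
- (d) If the interaction stays in the primary model, define its time coding and report only an estimable contrast. With categorical time that means quarters 2-7 only.

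The change in wording is small, but the confidence interval becomes wider than under a model that ignores time. A single indicator also assumes a constant effect over time. At about 223 patients per site-quarter, power for the diluted 2.4-point effect is about 0.5-0.6. The claim in section 7.1 that power stays above 0.80 should therefore be restated for the model chosen. Ignoring time shows 0.83-0.91 for the same effect, but that figure is valid only if there is no drift.
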